# 9.8 Internal Data and Safety Monitoring Board (DSMB)

A DSMB appointed by the National Institutes of Health not affiliated with the study will be responsible for evaluating the progress of the study and will be provided unblinded data on a regular basis to monitor patient safety. This committee will communicate by meeting monthly or as decided by the National Institutes of Health. Data will be reviewed by the DSMB in an unblinded fashion. Randomization codes for each enrolled patient will be provided to the DSMB as requested. The Committee will make its recommendations by monitoring progress, data, outcomes, toxicity, safety, and other confidential data, and may recommend stopping the clinical trial if an excessive number of serious adverse events are observed.

# 10 Data Handling and Record Keeping

# 10.1 Confidentiality

Information about study subjects will be kept confidential and managed according to the requirements of the Health Insurance Portability and Accountability Act of 1996 (HIPAA). Those regulations require a signed subject authorization informing the subject of the following:

- What protected health information (PHI) will be collected from subjects in this study.
- Who will have access to that information and why.
- Who will use or disclose that information.
- The rights of a research subject to revoke their authorization for use of their PHI.

In the event that a subject revokes authorization to collect or use PHI, the investigator, by regulation, retains the ability to use all information collected prior to the revocation of subject authorization. For subjects that have revoked authorization to collect or use PHI, attempts should be made to obtain permission to collect at least vital status (long term survival status that the subject is alive) at the end of their scheduled study period.

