### 4.5. Data Collection and Follow-Up for Withdrawn Subjects

- For withdrawn subjects (due to withdrawal of consent) not undergoing any study intervention, no additional follow-up will be done.
- For withdrawn subjects (due to withdrawal of consent) receiving Fisetin (Intervention), any additional evaluation will be for subject safety only. Research data will not be collected on subjects after withdrawal of consent.

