#### 8.2 Statistical Methods

All participants who are randomized will be included in the primary efficacy analysis. The analysis will follow the ITT principle (*i.e.* according to the treatment arm they are randomized to). For the primary analysis using the values of the 7-point scale, we will test the coefficient of the treatment effect (as a fixed effect) in an ordinal logistic regression model using a 2-sided 0.05 level Wald test after adjusting for key baseline variables such as baseline COVID severity status, age, and sex that show imbalance between the groups. Subjects who withdraw early but received at least some treatment will have their last known values carried forward until they complete the study at Day 180±14. All participants who receive any dose of drug (Fisetin or placebo) will be included in the safety and tolerability evaluation. The definitions of adverse events are described in Sections 9.1-9.3. Participants will be assessed over the entire period of drug administration. Frequency tables will be generated to summarize the occurrence of AE's by treatment arm. Comparisons of the rates of individual AEs will be done using tests of proportions such as the Fisher's exact test or Chi-squared test.

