# **8** Analysis plans for secondary endpoints:

- Rate- or proportion-based endpoints: Several measures will be evaluated in patients that will be summarized as incidence rates or the proportion of patients who have an event or incident of interest; e.g., mortality within 14 days. For these endpoints, we will calculate the proportions of patients who have these incident events of interest for each of the treatment arms and calculate 95% confidence intervals for these outcomes. These will be graphically and quantitatively compared using chi-square tests. Logistic regression models will be used to assess the influence of treatment arm on the incidence of these events while adjusting for other factors of interest.
- Time-to-event endpoints: Similarly, several measures will be analyzed in a secondary manner that will evaluate the distributions of the time to events of interest. These include time to hospital discharge, survival, or symptom improvement. For these outcomes, Kaplan-Meier methods will be used to graphically evaluate potential differences between treatment arms or other groups of interest. Further, these methods will be used to estimate median times as well as time-specific rates (*e.g.*, rate of transfer to hospital at 14 days). Cox proportional hazards models will be used to evaluate the influence of treatment arms, adjusting for other factors of interest.

- Oxygen supplementation and intubation: We will assess the incidence of oxygen supplementation or intubation and time to initiation of oxygen supplementation or intubation. In those who are given oxygen supplementation, we will summarize the duration of oxygen supplementation. Similarly, we will characterize and summarize the need for and duration of intubation. These will be analyzed in a manner similar to that described for the proportion/rate-based variables as well as the time-to-event variables but will specifically be based on a subset of patients given the nature of the outcome of interest. As such, these evaluations will be exploratory in nature.

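### Sections 4.5 and 10.1 are not reconciled on vital status after withdrawal and neither yields a date of death, so a dosed participant who withdraws alive and dies by Day 14 can be analysed at a living level

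*Combined protocol and SAP*

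**What the plan says.** Four parts of the combined protocol and SAP bear on this.

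- **Section 10.1 (revocation of authorization).** The investigator "retains the ability to use all information collected prior to the revocation of subject authorization". Beyond that, permission should be sought to "collect at least vital status (long term survival status that the subject is alive) at the end of their scheduled study period". Follow-up runs to Day 180±14.
- **Section 4.5 (withdrawal of consent).** "Research data will not be collected on subjects after withdrawal of consent". For withdrawn subjects receiving Fisetin, "any additional evaluation will be for subject safety only". Those who had no study intervention get no further follow-up. Withdrawn placebo recipients are not clearly placed under either rule.
- **Section 8.2 (analysis).** All randomized participants enter the primary analysis. "Subjects who withdraw early but received at least some treatment will have their last known values carried forward", up to Day 180±14. No exception is made for a death after withdrawal, and withdrawers who were never dosed are not mentioned.
- **Secondary endpoint plans.** Mortality within 14 days is given as an example of a proportion endpoint. Of the time-to-event endpoints the plan says: "These include time to hospital discharge, survival, or symptom improvement". Kaplan-Meier and Cox methods are named, but there is no censoring rule for withdrawals.

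The Study Summary and Section 8.1 set the primary endpoint at Day 14. Death is the worst of the seven levels in Section 2.1.

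**The concern.** Death is both the worst primary level and a secondary endpoint, so vital status is the most valuable fact to keep when a participant leaves. The plan gives two rules for that moment. One seeks vital status with permission and the other collects no research data. They concern different acts (revoking authorization and withdrawing consent), which will often happen together, and the plan does not say which rule then governs.

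Neither rule asks for what the analysis needs: whether the participant was alive at Day 14, and the date of any death. Nor does Section 8.2 say that a death learned of later replaces the carried-forward score.

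Participants may be enrolled through a legally authorized representative, who may withdraw them at any time for any reason (Sections 4.1 and 4.4.4). If withdrawal tends to come during decline, the hidden outcomes are disproportionately deaths. The documents do not say that it does; this is a plausible assumption. If it happened more in one arm, that arm would look better than it is.

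**Working it through.** **1. Follow one case through the text.** Take a participant dosed on Days 0 and 1 who withdraws alive on Day 5 and dies on Day 10.

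- Under 4.5, no research data are collected after Day 5. The death might surface through safety evaluation, but that is provided for only if the participant received Fisetin.
- Under 10.1, if authorization was also revoked and permission is given, a check near Day 180 finds the participant dead. It need not show whether death came before or after Day 14.
- Under 8.2, the last known value, a living level from Day 5 or before, is carried to Day 14 and on to Day 180.

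The Day 14 score is then a living level, and no rule corrects it even if the death becomes known.

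**2. Reproduce the plan's power.** Inputs from Section 8.1: 75 per arm, control probability 1/7 in each of seven levels, two-sided alpha 0.05, odds ratio 2.25. Proportional odds give Fisetin probabilities of 0.273, 0.201, 0.154, 0.122, 0.099, 0.082 and 0.069. Day 14 deaths are therefore 14.3% on control and 6.9% on Fisetin.

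Power = Φ(ln OR × √[(N/12)(1 − Σp̄³)] − 1.96), where p̄ is the two-arm mean at each level. With N = 150 and Σp̄³ = 0.0240, this is Φ(0.811 × √12.20 − 1.96) = Φ(0.872) = 80.9%. The stated 80% reproduces.

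**3. Deaths missed at Day 14.** Missed deaths = 150 × w × m, where w is the share who withdraw and m their later risk of death by Day 14. The documents give no w. For m, use 14.3% (planning distribution) up to 50% (top of the 25-50% mortality in Section 1.1, which carries no time limit).

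| Withdrawal w (assumed) | Missed deaths of 150 | Day 14 mortality understated by |
|---|---|---|
| 2% | 0.4 to 1.5 | 0.3 to 1.0 points |
| 5% | 1.1 to 3.8 | 0.7 to 2.5 points |
| 10% | 2.1 to 7.5 | 1.4 to 5.0 points |

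**4. Power.** Simulate the seven-level scale with the inputs in step 2, using a rank-sum test (close to the planned Wald test). Move a share of deaths in both arms to a random level from 2 to 5. Independent runs gave:

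| Share of Day 14 deaths hidden (assumed) | Power |
|---|---|
| none | about 80% |
| 10% | 0.4 to 1.3 points lower |
| 25% | about 78% (77.4% to 77.6%) |
| 50% | about 74% |

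The carried level matters. In a score approximation (base 79.2%), hiding 10% of deaths at level 4, 2 or 1 gives 78.6%, 77.0% or 75.4%.

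**5. Unequal hiding with no true effect.** With 50% of deaths hidden in one arm and 10% in the other, the 5% test rejects about 9% of the time, nearly always favouring the arm with more hidden deaths. With 25% against 10% it rejects 5.7%, and with 15% against 5%, 5.3%.

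**6. Survival, under one censoring choice.** Suppose every withdrawn survivor is credited to Day 180, every withdrawn death is censored at withdrawal, withdrawal is early, and mortality m is the same in those who withdraw. Estimated mortality is then (1 − w)m / [(1 − w) + w(1 − m)].

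- m = 0.25, w = 0.10: 0.225/0.975 = 23.1%, 1.9 points low.
- m = 0.50, w = 0.10: 0.450/0.950 = 47.4%, 2.6 points low.
- At w = 0.15 the shortfalls are 2.9 and 4.1 points.
- m = 0.40, w = 0.15 against 0.05: 36.2% against 38.8%, a false difference of 2.6 points.

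If everyone is censored at withdrawal instead, this particular bias does not arise.

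**The case against.** Several tempting stronger readings are not supported.

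- **That 10.1 seeks only confirmation of being alive.** It says at least vital status, which is a minimum, and a vital status check shows deaths too. Someone alive at Day 180 was alive at Day 14, and someone who died by Day 14 is found dead at Day 180. What is missing is the date and a rule for using it.
- **That 4.5 bars all collection.** It bars research data. Safety evaluation remains for withdrawn Fisetin recipients, and every death is a serious adverse event under Section 9.1.3.
- **That the two sections flatly contradict each other.** One concerns consent and the other authorization, so a default with a permission-based exception is a possible reading. The plan does not state it.
- **That survival is overstated.** This needs the asymmetric censoring in step 6, which the plan neither prescribes nor excludes. It also assumes that permission is always given.

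The affected group is also narrow. Those who only stop treatment stay in follow-up (4.4.2), transferred participants are followed wherever they are (3.3, 4.4.1), and a recorded death counts as withdrawal (4.4.4) and so carries forward as Death. The score error arises from carry-forward, which covers only dosed participants; the handling of undosed withdrawers is unstated.

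The larger figures need heavy withdrawal. Hiding half of a 14.3% death rate means 7.1% of an arm withdraws and then dies by Day 14. At 25% to 50% later mortality, 29% to 14% of that arm must withdraw (7.1/0.25 and 7.1/0.50). A false survival difference of 2.6 points is about a third of its standard error, √(2 × 0.4 × 0.6/75) = 8 points.

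All of this stands and limits the size. It does not remove the gap: the plan as written gives a wrong score to an identifiable kind of participant.

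**Conclusion.** The point holds in a limited form. Sections 4.5 and 10.1 need reconciling, neither provides for a date of death or Day 14 status, and 8.2 has no exception for death. A dosed participant who withdraws alive and dies by Day 14 would therefore be analysed at a living level, and Day 14 mortality would be understated.

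At modest withdrawal the effect is small: about 0.4 to 1.3 power points if 10% of deaths are hidden at middling levels, and more if the carried value is near the best level. It becomes material, at about 78% to 74% power, only if 25% to 50% of deaths are hidden. All these shares are assumptions. If nobody dies after leaving, the effect is zero.

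A reader might infer a bias in favour of Fisetin, but the direction between arms is unknown. Safety evaluation named only for Fisetin recipients could even reveal more deaths in that arm. This is an inexpensive improvement to the rules, not a defect that undermines the trial.

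**What to change.** - **Sections 10.1 and 4.5.** At withdrawal of consent or revocation of authorization, ask permission to record vital status at Day 14 and Day 180, with the date of any death, from nursing home, hospital or public records. Name this in 4.5 as the exception to the bar on research data, in the same words for both arms, dosed or not. A rule that turns on having received Fisetin is also hard for blinded staff to apply.
- **Section 8.2.** State that a known death by Day 14 overrides any carried-forward value and is scored as Death. State how undosed withdrawers are handled.
- **Time-to-event plan.** Use survival time after withdrawal only where status and date were sought alike for everyone who withdrew. Otherwise censor all of them at withdrawal.

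The cost is one line on the withdrawal form and a sentence or two in each section. Some participants or representatives will refuse; they remain censored for survival and carried forward for the primary score, so the gap shrinks but does not close. Reporting refusals by arm would show how much remains.

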#### 10.2 Source Documents

Source data is all information, original records of clinical findings, observations, or other activities in the clinical trial necessary for the reconstruction and evaluation of the trial. Source data are contained in source documents. Examples of these original documents, and data records include: nursing home records, hospital records, clinical and office charts, laboratory notes, memoranda, subjects' diaries or evaluation checklists, pharmacy dispensing records, recorded data from automated instruments, copies or transcriptions certified after verification as being accurate and complete, microfiches, photographic negatives, microfilm or magnetic media, x-rays, subject files, and records kept at the pharmacy, at the laboratories, and at medico-technical departments involved in the clinical trial.

### 10.3 Case Report Forms

The study case report form (CRF) is the primary data collection instrument for the study. Case reports in the form of completed checklists will be kept to assure inclusion/exclusion criteria and review of adverse events/toxicity. All data requested on the CRF will be recorded. All missing data must be explained. If a space on the CRF is left blank because the procedure was not done or the question was not asked, write "N/D". If the item is not applicable to the individual case, write "N/A". All entries will be printed legibly in black ink. If any entry error has been made, to correct such an error, a single straight line will be drawn through the incorrect entry and the correct data will be entered above it. All such changes will be initialed and dated. Errors will not be erased and "white-out" will not be used to correct errors. For clarification of illegible or uncertain entries, the clarification will be printed above the item, initialed, and dated. If the reason for the correction is not clear or needs additional explanation, details will be added related to the justification for the correction.

### 10.4 Data Management

The data will be housed in both hard copy case report forms (CRFs) and eCRFs.

### 10.5 Data Security and Confidentiality

Source documents and CRFs and original consents will be stored in secured locations. All data will be entered into a password protected, limited access database. Individually identifiable patient history and medical record information will be stored in a database under coded accession numbers. Clinical laboratory values will be stored in the electronic medical record system, requiring protected password access. These data are monitored regularly for access and a formal policy regarding protection of personal privacy is in place. The key to identification of subjects will be maintained in a secure office environment under the direction of the principal investigators.

### 10.6 Data Quality Assurance

Manual and computerized quality checks will occur during data collection and analyses and any

discrepancies will require Case Report Form (CRF) review and validation of correct data.

# 10.7 Records Retention

The investigator will maintain records and essential documents related to the conduct of the study. These will include subject case histories and regulatory documents. The sponsor-investigator will retain the specified records and reports for:

- 1. Until 2 years after the last shipment and delivery of the drug for investigational use is discontinued and the FDA has been so notified. OR
- 2. As outlined in the Mayo Clinic (and other participating institutions) Research Policy Manual –"Retention of and Access to Research Data Policy"

Whichever is longer.

# 11 Study Monitoring, Auditing, and Inspecting

# 11.1 Study Monitoring Plan

The investigator will allocate adequate time for such monitoring activities. The Investigator will also ensure that the monitor or other compliance or quality assurance reviewer is given access to all the study-related documents and study related facilities (*e.g.*, nursing home, pharmacy, diagnostic laboratory, *etc.*), and has adequate space to conduct the monitoring visit.

As a service to the sponsor-investigator, this study may be monitored during the conduct of the trial by staff from the Mayo Clinic Office of Research Regulatory Support (and other participating institutions). Clinical trial monitoring may include review of the study documents and data generated throughout the duration of the study to help ensure the validity and integrity of the data along with the protection of human research subjects. This will aid in complying with FDA regulations.

# 11.2 Auditing and Inspecting

The investigator will permit study-related monitoring, audits, and inspections by the IRB, the sponsor, and government regulatory agencies, of all study related documents (*e.g.*, source documents, regulatory documents, data collection instruments, study data, *etc.*). The investigator will ensure the capability for inspections of applicable study-related facilities (*e.g.*, nursing home, pharmacy, diagnostic laboratory, *etc.*).

Participation as an investigator in this study implies acceptance of potential inspection by government regulatory authorities and applicable compliance offices.

### 12 Ethical Considerations

This study will be conducted according to United States government regulations and Institutional research policies and procedures.

This protocol and any amendments will be submitted to a properly constituted local Institutional Review Board (IRB), in agreement with local legal prescriptions, for formal approval of the study. The decision of the IRB concerning the conduct of the study will be made in writing to the sponsor-investigator before commencement of this study.

All subjects for this study will be provided a consent form describing this study and providing sufficient information for subjects to make an informed decision about their participation in this study. This consent form will be submitted with the protocol for review and approval by the IRB

for the study. The formal consent of a subject, using the Approved IRB consent form, will be obtained before that subject undergoes any study procedure. The consent form will be signed manually or electronically by the subject or the subject's LAR and the individual obtaining the informed consent.

# 13 Study Finances

# 13.1 Funding Source

National Institutes of Health funding will be used to support this study.

#### 13.2 Conflict of Interest

Any study team member who has a conflict of interest with this study (patent ownership, royalties, or financial gain greater than the minimum allowable by their institution, *etc.*) must have the conflict reviewed by a properly constituted Conflict of Interest Committee with a Committee-sanctioned conflict management plan that has been reviewed and approved by the study sponsor-investigator prior to participation in this study.

### 13.3 Subject Stipends or Payments

Subjects will not receive remuneration.

# 14 Publication Plan

The principal investigators, Drs. [name] and [name], hold the primary responsibility for publication of the results of the study.

We will register with ClinicalTrials.gov within 21 days of the first subject being enrolled. We will post results to ClinicalTrials.gov within 12 months of final data collection for the primary outcome.

**COVID-FIS**: PILOT IN **COVID-**19 OF **FIS**ETIN TO REDUCE DYSFUNCTION AND INFLAMMATION IN NURSING HOME PATIENTS Version 7, Dated 26MAY2023

# **Appendix 1.** Ordinal Scale

# **Ordinal Scale for Clinical Improvement**

Patient State	Descriptor	Score	
Uninfected	No clinical or virological evidence of infection	0	
Ambulatory	No limitation of activities	1	
	Limitation of activities	2	
Hospitalized Mild disease	Hospitalized, no oxygen therapy	3	
	Oxygen by mask or nasal prongs	4	
Hospitalized Severe Disease	Non-invasive ventilation or high-flow oxygen	5	
	Intubation and mechanical ventilation	6	
	Ventilation + additional organ support – pressors, RRT, ECMO	7	
Dead	Death	8	

https://www.who.int/blueprint/priority-diseases/key-action/COVID-19 Treatment Trial Design Master Protocol synopsis Final 18022020.pdf

# **Appendix 2. Schedule of Events**

Procedures	Screening 	Baseline / Treatment	Treatment	Follow- up	Long-Term Follow-up		
Day(s)	-2 to 0	0 & 1	8 & 9	14 (±2 days)	30 (-2 to +7 days)	90 (±14 days)	180 (±14 days)
Verify Inclusion/Exclusion Criteria	Х	Х	Х				
Informed Consent	Х						
Demographics & Medical History	Х						
Randomization		Х					
IP Administration 		Х	Х				
Ordinal Scale	Х	Х	Х	Х	Х	Х	Х
Concomitant Medications 	Х	Х	Х	Х	Х	Х	Х
Adverse Events	Х	Х	Х	Х	Х	Х	Х
Vital Signs 	Х	Х	Х	Х	Х	Х	Х
MDS (as available)		Х			X	X	Х
Chest Imaging 	X	X	X	X	X	X	X
SARS-CoV-2	X						
Influenza & RSV Rapid Test	Х						
Safety Labs 	X			Х		Х	X
Research Labs  (blood and urine) & Biospecimens for Future Research Labs				X			

